After completing all study components, we will use a questionnaire (fp_Post-Study Questions) to ask participants a series of questions about their perceptions of the intervention, provide a short debriefing about study, and then ask whether or not they prefer to keep or remove the intervention depending on the condition they were assigned to.

If we are unable to reach a participant by phone after three attempts at any point throughout the study, we will mail them a letter asking them to contact us (fp_FoodPantryContactInfoFollowUpLetter).

Clean and track-changes Microsoft Word copies of this protocol are attached here (fp_FoodPantryIRBProtocol).

Staff Training and Protections

All study staff will complete HIPAA, GCP, CITI, and safe driving trainings before implementing this protocol. Study staff will use masks, practice social distancing, and use hand sanitizer and wash hands frequently.

Food pickups and deliveries and physical measurements will be contactless for as long as is required by University and government safety guidelines. Blood pressure cuffs, monitors, and scales are considered noncritical surfaces in health care because they only touch intact skin, and we will follow the recommendation to disinfect between each participant use.(2)

To ensure food safety, we will use cooler bags to store refrigerated and frozen items and make sure food is not in transport for long periods of time.

References

1. National Heart, Lung, and Blood Institute. Low Blood Pressure. National Institutes of Health, United States Department of Health and Human Services. <https://www.nhlbi.nih.gov/health-topics/low-blood-pressure>. Accessed December 14, 2020.
2. Havill NL. Best practices in disinfection of noncritical surfaces in the health care setting: Creating a bundle for success. Am J Infect Control. 2013;41(5 Suppl):S26-S30.

Pre-COVID-19 Procedures

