Are you conducting research outside of the United States?

No

Analysis Plan

Data will be descriptively summarized and evaluated for quality prior to the evaluation of primary and secondary endpoints. Means and standard deviations will be used to characterize continuous variables such as weight and blood pressure, and frequencies and percentages will be used to describe categorical variables such as nutritional quality. Medians and interquartile ranges will be reported for continuous variables that exhibit skewness. Data will be descriptively summarized overall and by condition. All outcomes will be analyzed at the customer level except for nutritional quality, which will be analyzed at the item level. Analyses will employ population-averaged marginal models estimated by Generalized Estimating Equations (GEE) to account for correlations among longitudinal monthly measurements and items purchased per food pantry customer. Marginal models estimated by GEE are advantageous for their population-level interpretation and robustness of estimated effects to the assumed correlation structure among repeated measurements (meaning unbiased estimates of the effect of the behavioral economic intervention will be obtained whether or not the correlation among repeated measurements within a food pantry customer is modeled correctly). Clusters will be defined at the level of the customer for all analyses, and independence working correlation will be assumed. Linear models will be used for continuous outcomes and logistic models for ordinal outcomes such as nutritional quality. Models will include 2-level intervention, month, and the interaction of intervention and month as categorical variables. The primary analysis of testing the effectiveness of the behavioral economic arm compared to the control arm will be evaluated by the joint test of the null hypothesis test that intervention-month interaction coefficients are 0, denoting no difference in the change in respective outcomes from baseline to month 3 between intervention groups. Secondary analyses will test for changes in intervention effects over time by testing whether intervention-month interaction coefficients are equivalent at month 3. We will evaluate the sensitivity of estimated intervention effects to imbalances in baseline covariates and missing data. To assess the impact of imbalance in baseline covariates, outcomes will be reanalyzed in models that adjust for baseline covariates that differ significantly at the 0.05 level by intervention arm. We will evaluate sensitivity to missing data by inverse probability of weighted GEE and multiple imputation. The Holm procedure⁷⁷ at a family-wise error rate of 0.05 will be used to account for multiple comparisons in testing differences in five primary outcomes between the two groups (nutritional quality of food selected, fruit and vegetable intake based on the food frequency questionnaire, weight, and blood pressure). Similar analyses of dermal carotenoids will be performed as secondary endpoint analyses.

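### With independence working correlation, the primary GEE is biased if baseline-related loss at month 3 differs between arms; the risk is material mainly for weight, and the planned methods that correct it are sensitivity analyses only

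*Combined protocol and SAP*

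**What the plan says.** All of the following is in the Analysis Plan. GEE is preferred partly because "unbiased estimates of the effect of the behavioral economic intervention will be obtained whether or not the correlation among repeated measurements" within a customer is specified correctly. The working structure is then fixed: "Clusters will be defined at the level of the customer for all analyses, and independence working correlation will be assumed". The mean model has no baseline covariate: "Models will include 2-level intervention, month, and the interaction of intervention and month as categorical variables". The primary test is that the interaction coefficients are zero, "denoting no difference in the change in respective outcomes from baseline to month 3 between intervention groups".

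Missing data appear once: "We will evaluate sensitivity to missing data by inverse probability of weighted GEE and multiple imputation". No variables are named for the weights or the imputation, and no rule says what follows if these analyses disagree with the primary one. The Holm procedure "at a family-wise error rate of 0.05 will be used to account for multiple comparisons in testing differences in five primary outcomes" is attached to the primary analysis.

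Under Study Procedures (Procedures), the physical measurements and the diet survey are taken at baseline and at 3 months only, and randomization follows the baseline measurements. The plan allows for lost contact: "If we are unable to reach a participant by phone after three attempts at any point throughout the study", a letter is sent. Subject compensation describes payments meant to support retention.

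**The concern.** A participant who misses the month-3 assessment stays in the baseline mean but leaves the month-3 mean. Under independence nothing in the estimator links the two, so the change in an arm mixes true change with a change in who is being averaged. If heavier participants in one arm are more likely to be missed, that arm appears to lose weight. Randomization balances baseline between the arms as randomized, but not between those still present at month 3.

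For an outcome with a wide spread between people and little change within a person, a small shift in composition can be large against the precision of the comparison. The confirmatory decision would then rest on the one planned analysis that makes no use of a non-returner's baseline value to correct the month-3 mean, while the two that can do so have no part in the Holm test.

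**Working it through.** **The plan's own figure.** None to reproduce: the documents give no power calculation, SD, within-person correlation or dropout rate.

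**Inputs from the documents.** 500 participants (Target population); two arms, allocation ratio not stated; two assessments; independence working correlation; saturated arm-by-month model; family-wise level 0.05 over five outcomes, so Holm's first step is 0.05/5 = 0.01.

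**Assumed inputs.** 250 per arm; 10% or 20% missing at month 3; odds of missing multiplied by 1.25 or 1.5 per SD of baseline in the intervention arm only; correlation ρ between baseline and month 3 of 0.5, 0.7 or 0.986. The last comes from a weight SD of 18 kg and an independent change SD of 3 kg: 18/√(18² + 3²) = 18/18.25 = 0.986. No true effect.

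**Step 1: what is estimated.** Under independence a saturated model reproduces the observed cell means, so the interaction is

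(observed month-3 mean − all-baseline mean) in intervention − the same in control.

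A fitted GEE on one simulated dataset with arm-specific loss gave -0.157, identical to this contrast. Exchangeable correlation on the same data gave -0.061. Once visits are missing, the choice of working correlation moves the point estimate.

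**Step 2: bias.** Let d be the mean standardized baseline of those still observed in an arm: d = E[z(1 − p(z))]/(1 − m), with z standard normal, p(z) the logistic probability of missing and m the overall loss. Then, in SD units,

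bias = ρ × (d_intervention − d_control).

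With loss unrelated to baseline in control, d_control = 0. By numerical integration at 20% loss, d_intervention = -0.0443 (odds ratio 1.25) or -0.0790 (1.5). At ρ = 0.986 this gives 0.986 × -0.0443 = -0.044 SD and 0.986 × -0.0790 = -0.078 SD, or about -0.8 and -1.4 kg at an SD of 18 kg.

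**Step 3: error rates.** Simulation with robust variance, 3,000 to 4,000 trials per scenario; a range is shown where repeat runs differed.

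| ρ | Loss | Odds ratio, one arm | Bias (SD) | Rejects at 0.05 | Rejects at 0.01 |
|---|---|---|---|---|---|
| 0.986 | 20% | 1.25 | -0.044 | 14–15% | 5% |
| 0.986 | 20% | 1.5 | -0.078 | 36–39% | 16–17% |
| 0.986 | 10% | 1.5 | -0.039 | 21–22% | 7% |
| 0.7 | 20% | 1.5 | -0.055 | 10% | 3% |
| 0.7 | 20% | 1.25 | -0.031 | 6–7% | 1–2% |
| 0.5 | 20% | 1.5 | -0.040 | 7% | 2% |
| 0.5 | 20% | 1.25 | -0.022 | 6% | 1% |

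**Step 4: when it vanishes, and when it does not.** With loss completely at random, or with the same dependence and the same rate in both arms, bias is 0 and error about 5%. With the same dependence (odds ratio 1.5) but 25% against 15% loss, at weight-like values, bias is about -0.7 kg and error 12–13%. Unequal rates are therefore enough once loss relates to baseline.

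**Step 5: the planned alternative.** Inverse-probability weighting with arm-specific weights on the baseline value left bias within simulation error of zero. At ρ = 0.986, 20% loss and odds ratio 1.5, it also cut the standard error from about 0.048 to 0.018 SD. A completers-only change score is not a general remedy: with 20% loss and a log-odds of 0.7 per SD in one arm, its bias was +0.062 SD at ρ = 0.5, because the retained group regresses toward the mean.

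**The case against.** Four points have force.

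First, a reader might infer that the plan claims immunity to dropout. It does not. The robustness sentence is about misspecifying the correlation, and missing data are treated later as a separate issue. The sentence lacks a condition; it makes no promise about loss.

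Second, both correcting methods are already planned. That limits the severity, but they have no part in the Holm decision and their models are unspecified.

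Third, a reader might infer that blood pressure and intake face the same inflation as weight, or take the 0.05 rates as the trial's error rate. Neither follows. The high rates need very strong tracking within a person, and the first Holm step is 0.01. At correlations of 0.5 to 0.7, which are possible for blood pressure and intake, the inflation under these scenarios is small.

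Fourth, differential loss is an assumption. The Design section says participants are not blinded, but also that they do not at first know of the other condition. Payments, training and contact are not described as differing by arm. The lost-contact letter is routine follow-up and does not forecast loss that differs by arm.

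What does not stand is that the order of the analyses is mere preference. In the weight-like scenario the weighted analysis removed the bias and was also more precise.

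**Conclusion.** The point holds as a conditional one. As specified, the primary analysis is valid with complete data or loss unrelated to the outcome, and its bias also cancels when baseline-related loss has the same pattern and rate in both arms. Otherwise it is biased, and materially so mainly for outcomes that track strongly within a person, weight being the clearest candidate.

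The size rests wholly on assumed dropout, slope and correlation values. The documents do not show that differential loss will occur, so it would be wrong to conclude that the trial's result will be biased, or that every primary outcome is at serious risk. Nutritional quality, analysed at item level, is outside these calculations.

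A change is worth making because the exposure is avoidable with methods already in the plan.

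**What to change.** For weight, blood pressure and screener intake, and for dermal carotenoids as a secondary endpoint:

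- Make the inverse-probability-weighted GEE or multiple imputation the primary analysis. Choose one in advance; for the primary outcomes, its result feeds the Holm test.
- Put the baseline value of the outcome, arm and their interaction in the weight or imputation model.
- Keep the unweighted independence GEE as a sensitivity analysis.
- Qualify the unbiasedness sentence: it applies with complete data or loss unrelated to the outcome.

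The cost is SAP wording and a reordering of analyses already planned, with no new data or visits. The small downside is reliance on the weight or imputation model. Neither method protects against loss that depends on the unobserved month-3 value; a delta-shift analysis within the imputation would probe that and is optional.

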Ukrainian translation was not done because we learned from the food pantry staff and our conversations with clients that the clients are largely English or Russian speaking and do not need Ukrainian language materials. Furthermore, the online ordering system at the food pantry is only available in English or Russian, so all clients shopping there must be able to communicate in one of those two languages. Finally, no clients to date have requested Ukrainian materials.

Attachments:

[fp_PostCards Recruitment_EN_v1.0_2020-12-14.pdf](#) (English post card)

[fp_PostCards Recruitment_RU_v1.0_2020-12-14.pdf](#) (Russian post card)

[fp_Translation for UPenn_RU_2020-12-14.pdf](#) (Certified Translation of PostCards Recruitment 2020-10-06_EN.pdf)

[fp_Poster_EN_v1.0_2020-12-14.pdf](#) (English poster, Certified Russian Translation to be included in subsequent modification)

Will the recruitment plan propose to use any Penn media services (communications, marketing, etc.) for outreach via social media avenues (examples include: Facebook, Twitter, blogging, texting, etc.) or does the study team plan to directly use social media to recruit for the research?

No

The following documents are currently attached to this item:

There are no documents attached for this item.

Subject compensation*

Will subjects be financially compensated for their participation?

Yes

The following documents are currently attached to this item:

There are no documents attached for this item.

If there is subject compensation, provide the schedule for compensation per study visit or session and total amount for entire participation, either as text or separate document

Prior to the COVID-19 pandemic, the study was conducted with three assessment points at baseline, 3-months, and 12-months. Since the pandemic, we have changed study protocols to only conduct assessments at baseline and 3-months. Participants who were enrolled prior to the pandemic who have not reached the 12-month time point have been notified that there will be no data collection at 12 months. For completing the assessments at baseline and 3-months, we will compensate participants \$25 for each visit. This incentive will be broken up into the following payments: \$10 for surveys, \$5 for blood pressure measurement, \$5 for weight measurement, and \$5 for veggie meter

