(diet quality) measurement. We will also remunerate participants \$25 for completing a training on how to use the pantry online ordering system. Participants will be paid via ClinCards. These are debit cards that we have successfully used in other longitudinal research studies that enable us to automatically load money onto a participants' card, which they can then use at any store like a debit card. We will also approve Check payments for participants who are unable to receive ClinCards. To strengthen cohort retention, we will incentivize successful online shopping each of the three months that participants are in the study after baseline measurements. For completing their baseline order, participants will receive a \$5 payment, for months 1 and 2, participants will receive \$3, and for month 3, participants will receive \$4, totaling \$15 for all orders. The total financial compensation for participation is \$90 (\$25 + \$25 + \$25 + \$15).

Prior to the COVID-19 pandemic, we planned to strengthen cohort retention during the study by entering each participant into several lotteries where 10 people had the chance of winning \$5 prizes and one person would win a \$100 prize. Because of the shortened timeline of the study (1 year to 3-months), we will no longer use a lottery to encourage cohort retention. We also planned to provide a \$3 incentive twice for participants confirming their contact information at 3-months and 12-months. Because of the shortened study timeline and that we will now incentivize shopping monthly, we will no longer provide a \$3 incentive for confirming contact information.

Study Procedures

Suicidal Ideation and Behavior

Does this research qualify as a clinical investigation that will utilize a test article (ie- drug or biological) which may carry a potential for central nervous system (CNS) effect(s)?

No

Procedures

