Following baseline measurements, participants will be randomized to one of two conditions: 1) the usual care group (control); or 2) the behavioral economic intervention.

To encourage participants to place orders using the food pantry's SmartChoice online ordering system, we will incentivize shopping by paying participants for successfully placing each order. We will train research participants on how to use the SmartChoice system via a walkthrough with study staff prior to their first order, for which they will be remunerated \$25. Participants will be remunerated for each order as follows: \$5 for baseline, \$3 for the first two months of participation, and \$4 for the third month of participation. We will provide printed online order guides to support online ordering (fp_Online Order Guide). We will also offer four months of contactless food delivery. Contactless means that when the Research Assistant brings the food to the study participant's home, they will place the food at the door, knock or ring the doorbell, and wait at a safe distance as the participant picks up the food. We will use phone and text messaging through Mosio, a secure text messaging platform, to communicate with participants using text message templates (fp_Text_Message_Templates).

Deliveries will only be offered to those participating in the study remotely, and for that reason we have removed any information about deliveries in our informed consent forms.

Three months after baseline, we will conduct 3-month measurements of weight, blood pressure, and diet quality using the Veggie Meter with participants at their homes or at the food pantry following all current COVID-19 safety guidelines. We will administer the diet survey again electronically through a REDCap survey. We will not administer the health survey at 3-months. We will provide the option of doing the survey over the phone on an as-needed basis for participants not comfortable with electronic surveys. Participants will receive \$25 for completing all components of 3-month measurements (\$10 for the survey, \$5 for blood pressure, \$5 for weight, and \$5 for veggie meter). We will provide participants with their blood pressure and weight results at the time of measurement using printed cards.

Food delivery will end after four months. We will use a post flyer to inform participants of their last food delivery (fp_PostCards Last Delivery).

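### For outcomes measured only at baseline and month 3, the primary model compares raw change instead of adjusting for the pre-randomization baseline value, which costs precision; missed month-3 visits could add a second loss under independence working correlation.

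*Combined protocol and SAP*

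**What the plan says.** The Analysis Plan gives one model form for all outcomes: "Models will include 2-level intervention, month, and the interaction of intervention and month as categorical variables". Continuous outcomes use linear models fitted by GEE, and "Clusters will be defined at the level of the customer for all analyses, and independence working correlation will be assumed". The primary test is that the arm-by-month interaction is zero, which the plan explains as equal change from baseline to month 3 in the two arms.

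Covariate adjustment appears only as a sensitivity analysis, in which "outcomes will be reanalyzed in models that adjust for baseline covariates that differ significantly at the 0.05 level by intervention arm". Missing data are also left to sensitivity analyses: "We will evaluate sensitivity to missing data by inverse probability of weighted GEE and multiple imputation". The Holm procedure at a family-wise 0.05 "will be used to account for multiple comparisons in testing differences in five primary outcomes between the two groups"; the list that follows names nutritional quality, questionnaire intake, weight and blood pressure. Dermal carotenoids are secondary.

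On timing, Subject compensation states: "Since the pandemic, we have changed study protocols to only conduct assessments at baseline and 3-months". The Procedures section gives the order of events: "Following baseline measurements, participants will be randomized to one of two conditions".

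**The concern.** With two visits and a linear model, arm, month and their interaction saturate the four cell means. The interaction coefficient is then exactly the difference between arms in mean change. Each arm keeps its own baseline mean, although randomization makes those means equal in expectation, so chance differences at baseline are carried at full weight into the estimate. Conditioning on the baseline value removes that noise without changing the target.

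The planned sensitivity reanalysis does not supply this. It is triggered by a significance test of imbalance, so a strongly prognostic baseline value that happens to be balanced would never be used. It also does not alter the Holm-tested result.

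The second issue is conditional. With complete data, independence working correlation costs nothing relative to modelling the correlation. If some month-3 values are missing and all available rows are analysed, everyone's baseline is compared with completers' month-3 values, and part of the within-person pairing is lost. The plan does not say whether customers without a month-3 value enter the primary model.

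At stake is power for three of the four named primary outcomes (intake, weight, blood pressure) and for the carotenoid endpoint. The documents contain no power calculation that would show there is power to spare.

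**Working it through.** **Inputs from the documents.** 500 participants (Target population); two assessments, with baseline before randomization (Procedures); family-wise 0.05 over five primary outcomes, so the smallest p-value is tested at 0.05/5 = 0.01 (Analysis Plan).

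**Assumptions, because the documents do not give them.** 250 per arm; two-sided tests; equal SD at both visits; correlation ρ between baseline and month 3, shown as a range; dropout completely at random, at 5% or 20%. There is no stated power figure to reproduce.

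**1. Complete data.** Per-person variances in SD² units:

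- Change: 2(1−ρ)
- Baseline-adjusted: 1−ρ²
- Ratio, adjusted to change: (1+ρ)/2, a cut of (1−ρ)/2

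With unequal SDs s0 and s1, the variance of change is s0² + s1² − 2ρ·s0·s1 and the adjusted variance is s1²(1−ρ²). The difference is (s0 − ρ·s1)², which is never negative.

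Example at ρ = 0.5 and a true difference of 0.25 SD:

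- Change: SE = √(2×1.00/250) = 0.0894, z = 2.80. Power is Φ(2.80−1.96) = 80% at 0.05 and Φ(2.80−2.576) = 59% at 0.01.
- Adjusted: SE = √(2×0.75/250) = 0.0775, z = 3.23. Power is 90% and 74%.

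| ρ | Variance cut | Change-score N matching 500 adjusted, 500×2/(1+ρ) | Power at 0.05, 0.25 SD | Power at 0.01, 0.25 SD |
|---|---|---|---|---|
| 0.4 | 30% | 714 | 72% → 86% | 49% → 68% |
| 0.5 | 25% | 667 | 80% → 90% | 59% → 74% |
| 0.6 | 20% | 625 | 88% → 94% | 71% → 82% |
| 0.7 | 15% | 588 | 95% → 97.5% | 85% → 91% |
| 0.8 | 10% | 556 | 99.3% → 99.7% | 97% → 98% |
| 0.98 | 1% | 505 | not computed | not computed |

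For a smaller difference of 0.20 SD at 0.01, power goes from 37% to 50% (ρ 0.5), 47% to 59% (0.6), 62% to 71% (0.7) and 83% to 87% (0.8).

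A simulation of 8,000 complete-data trials per scenario agrees. At 0.05 and 0.25 SD it gave 80.4% against 89.7% at ρ 0.5 and 95.2% against 97.5% at ρ 0.7. Null rejection was 4.3% to 5.2% for both methods. Adjustment spends one degree of freedom, about 0.2% of variance at this size, which would cancel the gain only at ρ of about 0.996 or more.

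**2. Missed month-3 visits.** With n = 250 and m = n(1−missing) per arm, the variance of the arm difference in SD² units is:

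- Independence, all rows: 2[1/m + (1−2ρ)/n]
- Complete pairs, change: 4(1−ρ)/m
- Modelled correlation, separate baseline means: 2[(1−ρ²)/m + (1−ρ)²/n]
- Baseline-adjusted: 2(1−ρ²)/m

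Example at ρ = 0.9, 20% missing (m = 200): independence 2[0.005 − 0.0032] = 0.0036; modelled 2[0.00095 + 0.00004] = 0.00198; ratio 1.82.

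| ρ | Independence / modelled, 5% missing | Independence / modelled, 20% missing | Complete pairs / modelled, 20% missing |
|---|---|---|---|
| 0.5 | 1.01 | 1.05 | 1.05 |
| 0.7 | 1.04 | 1.17 | 1.03 |
| 0.8 | 1.08 | 1.33 | 1.02 |
| 0.9 | 1.20 | 1.82 | 1.01 |
| 0.95 | 1.45 | 2.81 | 1.00 |
| 0.98 | 2.20 | 5.81 | 1.00 |

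**Illustration for weight** (assumed SD 18 kg, difference 1 kg = 0.056 SD, two-sided 0.05):

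| ρ | Missing | All rows, independence | Complete pairs | Baseline-adjusted |
|---|---|---|---|---|
| 0.98 | 20% | 21% | 79% | 80% |
| 0.95 | 20% | 18% | 42% | 43% |
| 0.90 | 20% | 15% | 24% | 25% |
| 0.98 | 5% | 53% | 86% | 86% |

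**The case against.** The planned analysis is not wrong. Difference in change is a legitimate prespecified hypothesis, and baseline is in the model as a response. The plan chooses GEE for its population-level interpretation and its robustness to a wrong correlation structure, and it claims no efficiency. No power target is missed, because none is stated. All of this stands: the point concerns precision only.

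The size cannot be fixed from the documents either. The largest gains need a correlation near 0.4, and no named outcome is shown to lie there. For a very stable measure such as weight, adjustment adds about one percentage point over complete pairs. The dramatic missed-visit figures need substantial dropout, very high correlation and all-rows analysis together. Retention may be good, since visits are paid and "To strengthen cohort retention, we will incentivize successful online shopping each of the three months". These limits also stand, and they are why ranges are shown and the second loss is kept conditional. They do not remove the case for a change that costs nothing and is never worse in large samples.

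Two matters of scope deserve care. The explicit order of baseline and then randomization appears in the current procedures; the Pre-COVID-19 Procedures do not state it. That section also says the Veggie Meter was introduced in October 2019, so some early participants may lack a baseline carotenoid value. A regression on baseline would drop them; a longitudinal model would keep them.

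**Conclusion.** The concern holds and should be fixed. The primary model for the two-visit outcomes gives up precision that is already paid for. With complete data and equal SDs, the variance saving is (1−ρ)/2: 10% to 25% for correlations of 0.8 down to 0.5, falling to 1% at 0.98. The second loss runs the other way: it is negligible at moderate correlation and large at very high correlation. It arises only if visits are missed and unpaired rows are analysed. Validity is unaffected under completely random dropout. The figures rest on 250 per arm, equal SDs and assumed correlations, effect sizes and dropout rates. The direction of the main point needs only large-sample theory and a baseline measured before randomization. Item-level nutritional quality is outside this point.

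**What to change.** For weight, blood pressure, questionnaire intake and dermal carotenoids, replace the primary model with one of the following:

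- **(a)** a regression of the month-3 value on arm and baseline value; or
- **(b)** a longitudinal model with a common baseline mean across arms and unstructured within-customer covariance, with robust standard errors. This also keeps customers who lack a baseline value.

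State whether customers without a month-3 value enter the primary analysis. Changing only the working correlation would restore pairing but would not deliver the baseline-adjustment gain. Keep the weighted GEE and multiple imputation as sensitivity analyses, and leave the nutritional quality analysis as planned. Confirm that baseline also preceded randomization for participants enrolled under the earlier procedures.

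The cost is a few sentences in the SAP and a different model statement, with no new data, participants or visits. Make the change before any unblinded analysis; the Design section says investigators and analysts remain blind to assignment.
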